## 7 Treatment Plan

### 7.1 Vitamin D and Calcium Supplementation

All subjects will receive a supplemental vitamin D (based on Vitamin D2+D3 levels beginning upon admission to the hospital for the HCT (54, 55). Vitamin D and Calcium supplementation will be determined by a combination of Vitamin D levels, ionized calcium levels, calcium intake, PTH, and TPN. See section 7.3 for supplementation guideline charts. In subjects who require parenteral nutrition (PN) and have normal vitamin D (D2+D3) level, vitamin D will be given as part of multivitamin supplementation.

- Adult multivitamin preparations contain 200 IU of cholecalciferol per 10 ml (or 5 mcg of ergocalciferol, equivalent to 200 IU of ergocalciferol, per 10 ml).

Pediatric multivitamin preparations contain 400 IU of cholecalciferol per 5 ml. (of 10 mcg of ergocalciferol, equivalent to 400 IU of ergocalciferol, per 5 ml)

If a subject's serum vitamin D (D2+ D3) is <30 ng/mL at any of the designated time points starting from study entry through Day 360 post-HCT (including 8 week rechecks for subtherapeutic levels), additional supplementation with vitamin D will be administered to maintain a serum level between 30 and 70 ng/mL according to the protocol as outlined in Section 7.

If serum vitamin D (D2+ D3) levels are low and supplementation is begun, levels will be re-checked after 8 weeks at the next scheduled study visit. Although the proposed regimen should normalize vitamin D level within 6-8 weeks (57), if the target range is not reached, supplementation will be continued for additional 8 weeks, and serum vitamin D level (D2+D3) repeated at the end of treatment. Subjects with vitamin D level (D2+D3) <20 ng/ml at Study Entry will be excluded from analyses of bone turnover markers until vitamin D level (D2+D3) normalizes but otherwise will be included in all analyses.

\*\* Measurement of Vit (D2+D3) levels is recommended instead of 25-hydroxy-Vitamin D level, as they reflect vitamin D stores accurately and independently of whether the subject is on VitD2 (ergocalciferol) or VitD3 (cholecalciferol) supplementation. As 25-hydroxyVitamin D assay mainly measures VitD3 stores, it can underestimate overall vitamin D stores in patients supplemented with

ergocalciferol (VitD2). However, 25-hydroxy Vitamin D assay can be used in patients who are on cholecalciferol supplementation.

†Per institutional practice, Fred Hutchinson Cancer Research center will measure 25-hydroxy-Vitamin D level.

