Vitamin D level (D 2 +D 3 ) †	10-19	
 
50000 IU (single dose) every week x 8 doses total
 
Vitamin D (D2+D3) level should be checked in 8 weeks
 
continue Vitamin D supplementation if still low
 
Once normalized the participant would receive 600 IU/day of Vitamin D
 
	
 
calcium supplementation at a dose of 50 mg/kg divided 3x/day (max daily calcium dose of 2,000 mg/day) for 4 weeks
 
After 4 weeks of calcium supplementation, if dietary calcium is low, the participant will receive calcium 1,200 mg/day
 

ionized or corrected calcium level	normal		
dietary calcium intake based on questionnaire	normal/low		
PTH*	>65		

**\*When PTH is <65 and Vitamin D level (D2+D3) is 10-20 with normal ionized or corrected calcium and normal or low dietary calcium intake, calcium supplementation at a dose of 50mg/kg/day 3 times daily is not needed, otherwise follow the same supplementation guidelines.**

Age	1-3 years	Vitamin D	Calcium (elemental)
Vitamin D level (D 2 +D 3 ) f	10-19	• 4000 IU/day of vitamin D supplementation x 8 weeks	• calcium supplementation at a dose of 50 mg/kg divided 3x/day (max daily calcium dose of 2.000 mg/day) for 4 weeks
ionized or corrected calcium level	low	• Vitamin D (D 2 +D 3 ) level should be checked in 8 weeks	• Check ionized or corrected calcium level every week and increase supplementation as needed to normalize ionized or corrected calcium
dietary calcium intake	normal or low	• continue Vitamin D supplementation if still low	• Once ionized or corrected calcium is normalized, if dietary calcium is low, the participant will receive calcium 600 mg/day
PTH*	>65	• Once normalized the participant would receive 600 IU/day of Vitamin D	

\* When PTH is <65 and Vitamin D level (D2+D3) is 10-19 with low ionized or corrected calcium and normal or low dietary calcium intake, follow the same supplementation guidelines.

Age	4-8 years	Vitamin D	Calcium (elemental)
Vitamin D level (D 2 +D 3 ) f	10-19		
ionized or corrected calcium level	low		
dietary calcium intake	normal or low		

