#### Laboratory Reference Ranges

	University of Minnesota (UMN)		Fred Hutchinson Cancer		
Creatinine (mg/dL)	0-21d	0.33-1.01	2 months-2 years	0.1-0.4	
	22 days-8 years	0.15-0.53			
	9-14 years	0.39-0.73		0.1-0.6	
	15-19y	0.5-1.0		0.2-0.9	
	20 y and older, F	0.52-1.04		0.2-1.1	
Calcium ("corrected calcium"?)	20 y and older, M	0.66-1.25	≥14 years	8.7-10.7	
	Age	mg/dL			
	0-11 mo	8.5-10.7			
	1-18 yr	9.1-10.3			
	19 yr & older	8.5-10.1			
Ionized Calcium	Age	mg/dL			
	0-11 mo	5.1-6.3			
	1 yr and older	4.4-5.2			
Vit D (D2 + D3) / 25-hydroxy (OH) vitamin D (ng/mL)	20-75		30-100		
Intact parathyroid hormone (iPTH) (pg/mL)	12-72pg/mL		12-75		
Interleukin (IL)-6 (pg/mL)	≤3.0		≤3.0		
IL-7 (pg/mL)	0.66-9.2		0.66-9.2		
Tumor necrosis factor alpha (TNF- $\alpha$ ) (pg/mL)	≤8.8		≤8.8		

a IL-6, IL-7, and TNF- $\alpha$  samples from Fred Hutchinson Cancer Research Center will be analyzed at UMN.

Laboratory normal ranges for CTX, DPD, P1NP, OCN, RANKL, and OPG vary with age. Urinary DPD will be adjusted for urinary creatinine content.

If total calcium or vitamin D (D2+D3)/25-OH vitamin D is below the normal range, supplementation will be administered per Section 7.3.

If creatinine level for a subject randomized to receive pamidronate becomes elevated during the study (creatinine level  $>2$  times the baseline value at Study Entry) refer to section 7.3.2 for treatment modification and monitoring.

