Control Group, but will decrease after initiation of pamidronate at Day 90 (Aim 3 Hypothesis 1), the test of changes up to Day 90 will use the same type of analysis as for Aim 2 Hypothesis 1 but with up to 5 measurements (Day -14 to Day 90). Tests of changes after Day 90 will include all available data for each subject and use a mixed linear model to account for correlation of measurements within subject; changes over time will be tested separately in the Pamidronate and Control groups using contrasts and compared between groups by testing the interaction of group and measurement time (i.e., Day 180, Day 360).

For the hypothesis that markers of bone formation, including osteocalcin (OCN) will decrease in the first three months and in the Control Group lower OCN levels at Day 90 will be associated with lower BMC and BMD 1 year post-HCT (Aim 3 Hypothesis 2), the test of change in OCN to Day 90 will use all available data and the same type of analysis as for Aim 2 Hypothesis 1; the test of change from Day 90 to Day 360 will use control subjects only and simple linear regression with outcome each of the BMC and BMD measures at Day 360 and predictor OCN level at Day 90.

For analyses of Aims 2 and 3 and Aim 1 hypothesis 2, further secondary analyses will use multiple imputation to impute missing measurements. Finally, exploratory analyses will explore risk factors for bone loss, including sex, BMI percentile, LBM adjusted for height, calcium and vitamin D intake, CNS radiation, TBI vs. no TBI in conditioning regimen, donor stem cell source (cord blood vs. other), physical activity, and glucocorticoid exposure for prophylaxis or treatment of GVHD. Subjects who experience a bone fracture after HCT will be excluded from analyses of bone turnover markers but otherwise will be included in all analyses.

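### Children with vitamin D below 20 ng/mL at Study Entry can enter the pre-Day 90 marker trend only at its last point, which biases the slope, up or down, if their markers still differ then

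*Combined protocol and SAP*

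**What the plan says.** Section 7.1 sets the exclusion: subjects below 20 ng/mL "at Study Entry will be excluded from analyses of bone turnover markers until vitamin D level" normalises. They stay in all other analyses. The same section says that low "levels will be re-checked after 8 weeks at the next scheduled study visit", and the deficiency charts in Section 7.3.3 repeat that the "level should be checked in 8 weeks".

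Section 8.1 schedules vitamin D at Screen or Study Entry and then at Days 90, 180, 270 and 360. CTX, P1NP, osteocalcin and urinary DPD are taken at Study Entry and Days 7, 14, 21, 90, 180 and 360.

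Section 12.4 tests early marker change with a mixed linear model (random intercept and time trend per child), "but with up to 5 measurements (Day -14 to Day 90"). After Day 90 it uses all available data and compares arms through the group-by-time interaction. It lists a fracture exclusion for marker analyses but does not mention the vitamin D rule.

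The rule does not say what counts as normal. Section 7.1 supplements to "maintain a serum level between 30 and 70 ng/mL"; Section 6.2 bars randomisation below 20 ng/mL.

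**The concern.** An exclusion that lasts until a condition clears works on visits, not on children. Here the condition can clear, on schedule, only after four of the five early marker draws. The first four points would then come from children who were not deficient at entry, and the fifth from those children plus the recovered ones. A lasting difference between the two kinds of child would appear in the model as change over time. The hypotheses at stake are that resorption markers rise and formation markers fall in the first three months.

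After Day 90 the same rule could make membership of a randomised comparison depend on a level measured after randomisation.

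**Working it through.** **1. The plan's own count.** Marker draws up to Day 90 in Section 8.1 are Study Entry and Days 7, 14, 21 and 90. That is 5, matching Section 12.4. Section 12.1 has 96 children at entry and 86 at Day 90 (96 × 0.9 = 86.4).

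**2. When an affected child can re-enter.** Supplementation starts at admission and the recheck is 8 weeks (56 days) later. Admission is assumed at Day -14 to -7, which puts 8 weeks at Day 42 to 49. That is after the Day 21 draw and before Day 90. A recheck by Day 21 would need admission by Day 21 - 56 = Day -35. An affected child therefore contributes at most 1 of 5 values.

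**3. Effect on the slope.** The documents do not give the deficient share *p*, the Day 90 marker difference *d* (in SD) or the intraclass correlation (ICC), so these are assumed. Total variance is 1 at Day 0, intercept variance is ICC, residual variance is 1 - ICC, and the random-slope SD is 0.3 per 100 days. The true slope is zero. Non-deficient children are seen at all five draws (those who die before Day 90 at four), deficient children at Day 90 only.

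- Expected estimate: β = (Σ X′V⁻¹X)⁻¹ Σ X′V⁻¹μ, with the slope scaled to the 104 days from Day -14 to Day 90.
- Two-sided rejection rate: 1 - Φ(1.96 - z) + Φ(-1.96 - z), with z = bias/SE.

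| *p* | *d* | ICC | Bias by Day 90 (SD) | SE | False positives |
|---|---|---|---|---|---|
| 15% | 0.5 | 0.7 | 0.030 | 0.090 | 6.3% |
| 15% | 1.0 | 0.5 | 0.091 | 0.111 | 13.1% |
| 30% | 0.5 | 0.7 | 0.060 | 0.096 | 9.6% |
| 30% | 0.5 | 0.5 | 0.092 | 0.118 | 12.3% |
| 30% | 1.0 | 0.7 | 0.121 | 0.096 | 24.0% |
| 30% | 1.0 | 0.5 | 0.185 | 0.118 | 34.9% |

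Example, last row: z = 0.185/0.118 = 1.57, and 1 - Φ(0.39) is about 0.35.

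The random intercept helps but is not enough. At *p* = 30% and *d* = 0.5 the raw Day 90 mean moves by 0.3 × 0.5 = 0.15 SD, and at ICC 0.5 the slope estimate keeps 0.092 SD of that. A fitted mixed model in that setting (200 simulated trials) gave a rise of 0.084 SD and 10% false positives, in line with the calculation.

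**4. Where the effect is small or absent.**
- *d* = 0.2: bias is proportional to *d*, so at *p* = 30% and ICC 0.5 it is 0.4 × 0.092 = 0.037 SD. Over *p* = 15-30% and ICC 0.5-0.7, false positives are 5.2-6.1%.
- Only half readmitted by Day 90 (assumed): 5.3-14% at 0.5-1.0 SD.
- *d* = 0: no bias. *d* = -0.5: a false fall of the same size as the rise.
- Affected children wholly in or wholly out: bias from this source is zero and the test stays at 5%.

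**5. After Day 90.** Consider a child below 20 ng/mL at entry:

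| Day 90 level (ng/mL) | Randomised? | Markers counted if normal means 20 | Markers counted if normal means 30 |
|---|---|---|---|
| below 20 | no (Section 6.2) | not applicable | not applicable |
| 20-29 | eligible on vitamin D | yes | no, until a later level |
| 30 or above | eligible on vitamin D | yes | yes |

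In the middle row, under the 30 reading, the next scheduled level is Day 180, which is after randomisation.

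**The case against.** The strongest case on the other side is that readmission requires the deficiency to have been corrected, which removes the most direct reason for a marker difference. The plan expects this: "Although the proposed regimen should normalize vitamin D level within 6-8 weeks". The documents give no deficiency rate and no marker difference. Section 8.3.5 notes that "Laboratory normal ranges for CTX, DPD, P1NP, OCN, RANKL, and OPG vary with age", but nothing says that deficiency at entry varies with age. This stands. The bias is a possibility whose size is assumed, and the upper end of the range needs the least favourable combination.

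The wording could also mean that all of a child's samples return once the level normalises. That reading removes the bias. The text does not say so, and an analyst cannot tell which is meant.

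Three stronger inferences are tempting and not supported:
- **That the rule produces a false rise.** The sign is unknown. If affected children run lower, the error is a false fall, which would matter for the formation-marker hypothesis.
- **That the site laboratory ranges supply two rival definitions of normal** (lower limit 20 at Minnesota, 30 at Fred Hutchinson). Section 7.1 sets one target for both sites and Section 7.3.2 treats 20-29 as low at both. The supportable point is that the exclusion rule cites neither the target nor the randomisation cutoff.
- **That any randomised child below 30 is at risk of exclusion.** Only those also below 20 at Study Entry are. Their Day 90 level is drawn before randomisation, so only the later readmission depends on post-randomisation data.

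**Conclusion.** The point holds in conditional form. On the plain reading, the sample changes at the last visit of the early trend. If the affected children's markers still differ at Day 90, the slope test is biased in a direction that the documents do not determine. With 15-30% deficient, 0.5-1.0 SD difference, ICC 0.5-0.7 and all normalised by Day 90, false positives are about 6-35% against 5%. With small differences or fewer readmitted the inflation is much smaller, and with no difference it vanishes.

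Separately, because normalisation is undefined, a randomised child below 20 at entry and at 20-29 on Day 90 may or may not be in the between-arm marker comparison. No size can be put on this from the documents.

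The reach is limited to secondary and correlative marker analyses. Section 7.1 keeps these children in everything else, so the primary comparison is untouched.

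**What to change.** Move the rule into Section 12.4 and apply it by child, not by visit:

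- **Study Entry to Day 90 trend, main analysis:** leave out entirely any child below 20 ng/mL at Study Entry.
- **Sensitivity analysis:** all children, all available draws, with a term for deficiency at entry.
- **Between-arm marker comparison after Day 90:** every randomised child, whatever the vitamin D level.

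Membership of these analyses then no longer depends on what the rule means by normalisation.

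The change is SAP wording only. Its cost is that the main early trend gives up the affected children's Day 90 values: 0.15 × 86 = 13 to 0.30 × 86 = 26 of 86 if 15-30% are deficient. Their earlier draws are already lost under the plain reading. The main result then describes children who were not deficient at entry; the sensitivity analysis brings the others back with all their visits.

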## 7.2 Calcium

Study subjects will be assessed to determine if supplemental calcium is warranted based on dietary intake and/or ionized calcium values. At the designated time points in the study starting at admission for the HCT through Day 360, dietary calcium intake will be determined from a Food Frequency Questionnaire (FFQ) (Appendix II). Subjects who do not meet the RDA will receive additional calcium supplementation (Section 7.3).

At the designated time points in the study starting at admission for HCT through Day 360, ionized calcium or corrected calcium, and vitamin D (D2+D3) levels will be assessed. If the subject's level is below the normal range at any time, supplemental calcium and vitamin D supplementation will be given per Section 7.3

*If a subject's total calcium level is below the normal range at any time, calculate a corrected calcium if a serum albumin level is available (may have been drawn anytime within 7 days of the calcium level) using the formula:*

***Corrected Ca = measured total Ca + [0.8 (4.0 - serum albumin mg/dL)]***

*If a serum albumin level is not available ionized calcium level should be done.*

If a subject's vitamin D level (D2+D3) is 10-20 ng/mL and their iPTH level is >65 pg/mL or if vitamin D level (D2+D3) is <10 ng/mL at any time from Study Entry through Day 360, additional calcium carbonate will be administered per Section 7.3.

## 7.3 Vitamin D and Calcium Supplementation Charts:

*For all dosing, these charts list the ideal targeted dose, however dosing will be in an acceptable range as set by available formulations or insurance barriers*

†Per institutional practice, Fred Hutchinson Cancer Research center will measure 25-hydroxy-Vitamin D level

### 7.3.1 For Vitamin D Sufficient Patients

Age	All	Vitamin D	Calcium (elemental)
Vitamin D level (D 2 +D 3 ) T	sufficient	600 IU/day of Vitamin D supplementation only	No Supplementation
ionized or corrected calcium level	normal		
dietary calcium intake based on questionnaire	sufficient		

Age	1-3 years	Vitamin D	Calcium (elemental)
Vitamin D level (D 2 +D 3 ) T	sufficient	600 IU/day of Vitamin D	600 mg/day
ionized or corrected calcium level	normal		
dietary calcium intake based on questionnaire	low		

Age	4-8 years	Vitamin D	Calcium (elemental)
Vitamin D level (D 2 +D 3 ) T	sufficient	600 IU/day of Vitamin D	1,000 mg/day
ionized or corrected calcium level	normal		
dietary calcium intake based on questionnaire	low		

Age	≥ 9 years	Vitamin D	Calcium (elemental)
Vitamin D level (D 2 +D 3 ) T	sufficient	600 IU/day of Vitamin D	1,200 mg/day
ionized or corrected calcium level	normal		
dietary calcium intake based on questionnaire	low		

Age	1-3 years	Vitamin D	Calcium (elemental)
Vitamin D level (D 2 +D 3 ) T	sufficient	• 600 IU/day Vitamin D	• calcium supplementation at a dose of 50 mg/kg divided 3x/day day (max daily calcium dose of 2000 mg/day). • Check levels weekly, increase as needed to normalize ionized or corrected calcium. • Once normalized, if dietary calcium intake is low the participant would receive calcium 600 mg/day
ionized or corrected calcium level	low		
dietary calcium intake based on questionnaire	Low or normal		

Age	4-8 years	Vitamin D	Calcium (elemental)
Vitamin D level (D 2 +D 3 ) T	sufficient	• 600 IU/day Vitamin D	• calcium supplementation at 50 mg/kg divided 3x/day day (max daily calcium dose of 2000 mg/day). • Check levels weekly, increase as needed to normalize ionized or corrected calcium. • Once normalized, if dietary calcium intake is low the participant would receive calcium 1,000 mg/day
ionized or corrected calcium level	low		
dietary calcium intake based on questionnaire	Low or normal		

Age	$\geq 9$ years	Vitamin D	Calcium (elemental)
Vitamin D level ( $D_2+D_3$ ) f	sufficient	• 600 IU/day Vitamin D	• calcium supplementation at 50 mg/kg divided 3x/day (max daily calcium dose of 2000 mg/day).
ionized or corrected calcium level	low		• Check levels weekly, increase as needed to normalize ionized or corrected calcium.
dietary calcium intake based on questionnaire	Low or normal		• Once normalized, if dietary calcium intake is low the participant would receive calcium 1,200 mg/day

### 7.3.2 For Low vitamin D ( $D_2+D_3$ ) Levels

Age	$<9$	Vitamin D	Calcium (elemental)
Vitamin D level ( $D_2+D_3$ ) f	20-29	• 4000 IU/day of vitamin D supplementation x 4 weeks	• No supplementation
ionized or corrected calcium level	normal		
dietary calcium intake based on questionnaire	sufficient	• Vitamin D ( $D_2+D_3$ ) level should be checked in 4 or 8 weeks and continue supplementation if needed • Once the Vitamin D level is normalized the participant would receive 600 IU/day of Vitamin D	

Age	$\geq 9$	Vitamin D	Calcium (elemental)
Vitamin D level ( $D_2+D_3$ ) T	20-29	
 
• 4000 IU/day of vitamin D supplementation x 8 weeks
 
	
 
• No supplementation
 

ionized or corrected calcium level	normal	
 
• Vitamin D (<math>D_2+D_3</math>) level should be checked in 4 or 8 weeks and continue supplementation if needed
 
	
dietary calcium intake based on questionnaire	sufficient	
 
• Once the Vitamin D level is normalized the participant would receive 600 IU/day of Vitamin D
 
	

Age	1-3 Years	Vitamin D	Calcium (elemental)
Vitamin D level ( $D_2+D_3$ ) T	20-29	
 
• 4000 IU /day of vitamin D supplementation x 4 weeks
 
	
 
• calcium 600 mg/day
 

ionized or corrected calcium level	normal	
 
• Vitamin D (<math>D_2+D_3</math>) level should be checked in 4 or 8 weeks and continue supplementation if still low
 
	
dietary calcium intake based on questionnaire	low	
 
• Once the Vitamin D level is normalized the participant would receive 600 IU/day of Vitamin D
 
	

Age	4-8 years	Vitamin D	Calcium (elemental)
Vitamin D level (D 2 +D 3 ) T	20-29	
 
• 4000 IU/day of vitamin D supplementation x 4 weeks
 
• Vitamin D (D2+D3) level should be checked in 4 or 8 weeks and continue supplementation if still low
 
• Once the Vitamin D level is normalized the participant would receive 600 IU/day of Vitamin D
 
	
 
• calcium 1,000 mg/day
 

ionized or corrected calcium level	normal		
dietary calcium intake based on questionnaire	low		

Age	$\geq 9$	Vitamin D	Calcium (elemental)
Vitamin D level (D 2 +D 3 ) T	20-29	
 
• 4000 IU/day of vitamin D supplementation x 8 weeks; or 50000 IU (single dose) of vitamin D every other week x 4 doses total
 
• Vitamin D (D2+D3) level should be checked in 4 or 8 weeks and continue supplementation if still low
 
• Once the Vitamin D level is normalized the participant would receive 600 IU/day of Vitamin D
 
	
 
• calcium 1,200 mg/day
 

ionized or corrected calcium level	low		
dietary calcium intake based on questionnaire	Low or normal		

Age	1-3 years	Vitamin D	Calcium (elemental)
Vitamin D level (D 2 +D 3 ) T	20-29	
 
4000 IU/day of vitamin D supplementation x 4 weeks
 
	
 
calcium supplementation at 50 mg/kg divided 3x/day day (max daily calcium dose of 2000 mg/day).
 

ionized or corrected calcium level	low	
 
Vitamin D (D2+D3) level should be checked in 4 or 8 weeks and continue supplementation if still low
 
	
 
Check levels weekly, increase as needed if low.
 

dietary calcium intake based on questionnaire	Low or normal	
 
Once the Vitamin D level is normalized the participant would receive 600 IU/day of Vitamin D
 
	
 
Once ionized or corrected calcium is normalized, if dietary calcium is low, the participant would receive calcium 600 mg/day
 

Age	4-8 years	Vitamin D	Calcium (elemental)
Vitamin D level (D 2 +D 3 ) T	20-29	
 
4000 IU/day of vitamin D supplementation x 4 weeks
 
	
 
calcium supplementation at 50 mg/kg divided 3x/day day (max daily calcium dose of 2000 mg/day).
 

ionized or corrected calcium level	low	
 
Vitamin D (D2+D3) level should be checked in 4 or 8 weeks and continue supplementation if still low
 
	
 
Check levels weekly, increase as needed if low.
 

dietary calcium intake based on questionnaire	Low or normal	
 
Once the Vitamin D level is normalized the participant would receive 600 IU/day of Vitamin D
 
	
 
Once ionized or corrected calcium is normalized, if dietary calcium is low, the participant would receive calcium 1,000 mg/day
 

Age	$\geq 9$	Vitamin D	Calcium (elemental)
Vitamin D level ( $D_2+D_3$ ) T	20-29	
 
4000 IU/day of vitamin D supplementation x 8 weeks; or 50000 IU (single dose) of vitamin D every other week x 4 doses total Vitamin D (<math>D_2+D_3</math>) level should be checked in 4 or 8 weeks and continue supplementation if still low
 
Once the Vitamin D level is normalized the participant would receive 600 IU/day of Vitamin D
 
	
 
calcium supplementation at a dose of 50 mg/kg divided 3x/day (max daily calcium dose of 2000 mg/day).
 
Check levels weekly, increase as needed if low.
 
Once ionized or corrected calcium is normalized, if dietary calcium is low, the participant would receive calcium 1,200 mg/day
 

ionized or corrected calcium level	normal		
dietary calcium intake based on questionnaire	low		

Age	$< 9$	Vitamin D	Calcium (elemental)
Vitamin D level ( $D_2+D_3$ ) T	20-29	
 
50000 IU (single dose) of vitamin D every other week x 2 doses total
 
Check Vitamin D (<math>D_2+D_3</math>) levels in 4 weeks
 
Continue vitamin D supplementation until Vitamin D levels normalize. Once normalized vitamin D would be given as part of multivitamin supplementation.
 
	
 
calcium supplementation at a dose of 50 mg/kg/day (max daily calcium dose of 2000 mg/day) or the maximum allowed per TPN
 
Check ionized or corrected calcium level every week
 

ionized or corrected calcium level	low		
Patient on TPN	Yes		

Age	$\geq 9$	Vitamin D	Calcium (elemental)
Vitamin D level ( $D_2+D_3$ ) T	20-29	
 
50000 IU (single dose) every other week x 4 doses total
 
	
 
calcium supplementation a dose of 50 mg/kg/day (max daily calcium dose of 2000 mg/day) or the maximum allowed per TPN
 

ionized or corrected calcium level	low	
 
Check Vitamin D (<math>D_2+D_3</math>) levels in 8 weeks
 
Continue vitamin D supplementation until Vitamin D levels normalize. Once normalized vitamin D would be given as part of multivitamin supplementation.
 
	
 
Check ionized or corrected calcium level every week
 

Patient on TPN	Yes		

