PTH*	>65	
 
• 4000 IU/day of vitamin D supplementation x 8 weeks
 
• Vitamin D (D2+D3) level should be checked in 8 weeks
 
• continue Vitamin D supplementation if still low
 
• Once normalized the participant would receive 600 IU/day of Vitamin D
 
	
 
• calcium supplementation at a dose of 50 mg/kg divided 3x/day (max daily calcium dose of 2.000 mg/day) for 4 weeks
 
• Check ionized or corrected calcium level every week and increase supplementation as needed to normalize ionized or corrected calcium
 
• Once ionized or corrected calcium is normalized, if dietary calcium is low, the participant will receive calcium 1,000 mg/day
 

**\* When PTH is <65 and Vitamin D level (D2+D3) is 10-19 with low ionized or corrected calcium and normal or low dietary calcium intake, follow the same supplementation guidelines.**

Age	$\geq 9$	Vitamin D	Calcium (elemental)
Vitamin D level ( $D_2+D_3$ ) T	10-19	
 
• 50000 IU (single dose) every week x 8 total doses
 
• Vitamin D (<math>D_2+D_3</math>) level should be checked in 8 weeks
 
• Continue Vitamin D supplementation if still low
 
• Once normalized the participant would receive 600 IU/day of Vitamin D
 
	
 
• calcium supplementation at a dose of 50 mg/kg divided 3x/day (max daily calcium dose of 2.000 mg/day) for 4 weeks
 
• Check ionized or corrected calcium level every week and increase supplementation as needed to normalize ionized or corrected calcium
 
• Once ionized or corrected calcium is normalized, if dietary calcium is low, the participant will receive calcium 1,200 mg/day
 

ionized or corrected calcium level	low		
dietary calcium intake	normal or low		
PTH*	$>65$		

***\*When PTH is  $<65$  and Vitamin D level ( $D_2+D_3$ ) is 10-19 with low ionized or corrected calcium and normal or low dietary calcium intake, follow the same supplementation guidelines.***

Age	<9	Vitamin D	Calcium (elemental)

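### Two calcium charts for age 9 and over (vitamin D 20-29, not on TPN) carry each other's conditions, so a child with low serum calcium gets a flat 1,200 mg/day with no weekly recheck or titration

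*Combined protocol and SAP*

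**What the plan says.** Section 7.3 sets the calcium dose by age, vitamin D level, serum (ionized or corrected) calcium and dietary intake. For age 9 and over, vitamin D 20-29 and no TPN, Section 7.3.2 has three charts. One (normal serum calcium, sufficient diet, no calcium given) is not in question. The other two are:

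- **Flat-dose chart.** Printed condition: serum calcium low, diet low or normal. The whole calcium instruction is "calcium 1,200 mg/day". The only recheck in the chart is of vitamin D: "level should be checked in 4 or 8 weeks and continue supplementation if still low".
- **Weight-based chart.** Printed condition: serum calcium normal, diet low. It orders 50 mg/kg in three daily portions, capped at 2,000 mg/day, with weekly checks and an increase if low. It then steps down: "Once ionized or corrected calcium is normalized, if dietary calcium is low, the participant would receive calcium 1,200 mg/day".

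The vitamin D instructions of the two charts have the same content, so only calcium dosing and calcium monitoring differ. Section 7.2, Section 7.4.1 and footnote f of the schedule in Section 8.1 all send a low calcium result to Section 7.3.

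**The concern.** The weight-based chart contradicts its own label, because a calcium level that is already normal cannot be the trigger for a step-down once it becomes normal. The flat-dose chart treats a documented low serum calcium as if it were only a dietary shortfall.

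The error bears on safety because these charts are the protocol's stated response to low calcium. Section 7.4.1 lists only creatinine and pregnancy as reasons to hold pamidronate; for a low pre-infusion calcium it orders supplementation under Section 7.3. Section 6.2 bars randomization for vitamin D below 20, so a child at 20-29 can be randomized. Section 7.4.3 calls hypocalcemia common in children given pamidronate, and Section 1.2 names calcium and vitamin D supplementation as the way to prevent or mitigate it. In this cell, a site that follows the protocol exactly gives the less intensive regimen to the child who needs the more intensive one.

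**Working it through.** The plan gives no summary figure to reproduce here. The check compares charts, then works out the dose consequence.

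**1. Comparable charts.** All are from Section 7.3.

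| Chart | Serum calcium | Calcium instruction |
|---|---|---|
| 7.3.1, age 9 and over | normal, diet low | flat 1,200 mg/day |
| 7.3.1, age 9 and over | low | 50 mg/kg; "Check levels weekly, increase as needed to normalize ionized or corrected calcium"; then "Once normalized, if dietary calcium intake is low the participant would receive calcium 1,200 mg/day" |
| 7.3.2, ages 1-3 and 4-8 | normal, diet low | flat 600 or 1,000 mg/day |
| 7.3.2, ages 1-3 and 4-8 | low | 50 mg/kg, weekly checks, step-down |
| 7.3.2, age 9 and over, on TPN | low | 50 mg/kg daily, or as much as TPN allows; "Check ionized or corrected calcium level every week" |
| 7.3.3, age 9 and over, not on TPN | low | 50 mg/kg; "Check ionized or corrected calcium level every week and increase supplementation as needed to normalize ionized or corrected calcium" |
| **7.3.2, age 9 and over, not on TPN** | **low** | **flat 1,200 mg/day** |
| **7.3.2, age 9 and over, not on TPN** | **normal, diet low** | **50 mg/kg, weekly checks, step-down** |

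**2. Counts.**

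- Charts labelled only low for serum calcium: three in 7.3.1, five in 7.3.2 (two of them TPN) and three in 7.3.3, so 3 + 5 + 3 = 11. Ten give 50 mg/kg with weekly checks. The flat-dose chart is the sole exception.
- Charts with normal serum calcium and low diet at vitamin D 20 or above: three in 7.3.1 and three in 7.3.2, so 6. Five give a flat dose without a weekly check. The weight-based chart is the sole exception.
- A weight-based dose for normal serum calcium is not by itself an error: the three 7.3.3 charts for vitamin D 10-19 with PTH above 65 also use one. The weekly check and the step-down on normalization are what mark this chart. They appear in 1 of the 12 charts labelled only normal (4 + 5 + 3 across 7.3.1 to 7.3.3).

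Exchanging the two pairs of conditions makes both counts complete: 11 of 11 and 6 of 6.

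**3. Dose for a low-calcium child.** Intended dose = min(50 mg/kg × weight, 2,000 mg) per day; printed dose = 1,200 mg per day. I read 50 mg/kg as a daily total, because the 7.3.4 chart for age 9 and over states it per day. The documents give no weights, so those below are assumptions.

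- Equal doses: 1,200 / 50 = 24 kg. Cap reached: 2,000 / 50 = 40 kg.
- 20 kg: 1,000 intended; printed is 200 / 1,000 = 20% more.
- 25 kg: 1,250 intended; printed is 50 / 1,250 = 4% less.
- 30 kg: 1,500 intended; printed is 300 / 1,500 = 20% less.
- 35 kg: 1,750 intended; printed is 550 / 1,750 = 31% less.
- 40 kg or more: 2,000 intended; printed is 800 / 2,000 = 40% less.

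**4. Monitoring.** The other low-serum charts recheck calcium every 7 days. Without that, the next visit calcium in Section 8.1 is 180 − 90 = 90 days after Day 90 and 270 − 180 = 90 days after Day 180. From entry (Day −14 in the Section 12.1 table) to Day 90 it is 104 days, all before any pamidronate. Pamidronate patients also have an end-of-infusion calcium on each infusion day.

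**5. Reach.** Section 12.3 plans one third of enrollment at age 10 or over, and Section 12.1 expects 86 children at Day 90. Taking age 10 as a rough stand-in for age 9 and assuming equal arms, 86 / 3 ≈ 29 children, about 14 of them on pamidronate. Only those with vitamin D 20-29, low serum calcium and no TPN meet this chart, and the documents do not say how many that is.

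**The case against.** The strongest reply is that this is a clerical slip that a clinician would notice, surrounded by safeguards. Much of that stands. Calcium is scheduled at entry and at Days 90, 180 and 270. In pamidronate patients it is drawn before each infusion and again before discharge, and Section 7.4.1 asks specifically for a post-infusion ionized or corrected level in children on supplemental calcium. These patients also have a telephone adverse-event assessment one week after each infusion. Section 8.2.6 allows unscheduled visits, Section 7.4.3 points to intensive post-transplant monitoring, and Section 7.4.6 lets the investigator stop the drug. A reader might infer that a low-calcium child in this cell has no calcium recheck at all. The documents do not support that; what is lost is the weekly check and the instruction to raise the dose. None of the safeguards restores these, and the Section 7.2 rule for a low level at any time leads back to the same chart.

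The tables could also have been damaged in text extraction. That is unlikely: two intact charts lie between the pair, and each set of conditions fits the other chart's instructions.

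The dose effect depends on weight and reverses below 24 kg. That is correct, but the loss of weekly titration applies at every weight.

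**Conclusion.** The point holds. In one age and vitamin D cell of Section 7.3.2, the calcium conditions of two charts are exchanged with each other, and no other text corrects them. Followed as printed, a child with low serum calcium loses weekly rechecking and titration and, on assumed weights, gets 20% less calcium at 30 kg and 40% less at 40 kg or more. This rests on reading 50 mg/kg as a daily total. The number of children is unknown and probably small.

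Three stronger readings should be resisted:

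- The serum and dietary rows are not transposed inside a chart. The pair of conditions as a whole sits on the wrong chart.
- A reader might infer lasting over-supplementation of the child with normal calcium and low intake. The printed dose can exceed 1,200 mg/day by up to 800 mg, but the step-down returns that child to 1,200 mg/day once calcium is found normal.
- A reader might infer harm to the trial's result. Supplementation under Section 7.3 applies to both arms, and nothing here touches the sample size, the primary analysis or the treatment comparison. This is a safety and dosing error.

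**What to change.** In Section 7.3.2, age 9 and over, vitamin D 20-29, not on TPN, exchange the calcium condition cells between the two charts:

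- the 1,200 mg/day chart becomes serum calcium normal, diet low;
- the 50 mg/kg chart with weekly checks becomes serum calcium low, diet low or normal.

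Leave the vitamin D and calcium instructions as they are. Send the sites a memo with the corrected charts.

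The cost is a wording amendment and the memo. No new type of test is needed. Weekly calcium checks would apply only to low-calcium children in this cell, as the comparable charts already require, and would no longer be ordered for those whose calcium is normal.
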